- An anthracycline; either daunorubicin , idarubicin or mitoxantrone at standard doses daily for 3 days, starting on day 1.

The second induction will consist of dose-adjusted high dose Ara-C alone (1-1.5grm/m² Q12 hrs on day 1, 3, and 5, per standard of care). The timing for initiation of the second induction depends upon results of marrow done 14-21 days after the first induction according to standard of care practice.

- Patients who do not achieve remission at the conclusion of 2 inductions will be considered screen failures and offered alternative therapies.

Consolidation:

- Omacetaxine 1.25 mg/m² sub-cutaneously twice daily for 5 consecutive days every 28 (\pm 8) days for a total of 3 cycles.

Maintenance:

- Subjects in continuous remission after 3 cycles of consolidation with omacetaxine will receive maintenance omacetaxine 1.25mg/m² twice daily for 3days, every 28 days, for up to 6 cycles.

Sample size and patient selection:

- **Screening:** 45 patients with newly diagnosed, untreated AML eligible for induction chemotherapy. Patients who received 1-2 cycles of hypomethylating therapy for cytoreduction are also eligible.
- **Consolidation/maintenance:** 15 patients in first complete remission after 2 inductions.

Assessment of response:

- Bone marrow biopsy and aspirate will be obtained at day 14-21 of the 1st cycle, and at day 28 or at count recovery, whichever occurs first.
- Prior to each consolidation cycle, responses will be evaluated with a complete blood count (CBC) and bone marrow aspiration/biopsy to document continued remission.
- Bone marrow aspirate to confirm continuous remission will be obtained every 3 months during maintenance, and as clinically indicated thereafter.

Statistical Methods:

- This study is an open label, pilot study. Continuous data will be described using descriptive statistics (n, mean, median, minimum, and maximum) while discrete data will be described using frequency counts and percentages.

Time line: 2-3 years, based on previous accrual in the target population.

1. BACKGROUND:

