High dose cytarabine (HiDAC, doses $> 1.5 \text{ g/m}^2/\text{d}$) administered during induction results in improved recurrence-free and overall survival in younger AML patients < 60 ,¹² but is associated with increased toxicities in older patients^{13,14}. We have recently reported on the safety and efficacy of modified HiDAC induction for newly diagnosed patients ≥ 60 with AML ([name] et al. ASCO 2010). HiDAC induction was well-tolerated, associated with high CR rates (69%), and comparable early mortality to standard dose cytarabine induction (19%). In our series, 37/59 (63%) patients were able to receive the 2 planned inductions. Of the 41/59 (69%) that achieved remission, 6, 11, and 10 patients received 1, 2, and 3 consolidations with HiDAC, respectively. **However, despite high initial CR rate (69%) and the delivery of standard consolidation in 80%, the median relapse-free survival was 11 months, and most patients died from relapsed leukemia.** Therefore, exploring alternative consolidation regimens is desirable. Since the current study opened, we have learned that prospectively, our patients did not tolerate the 2 consecutive cycles of modified HiDAC/daunorubicin due to cardiac toxicity, and have amended the protocol to limit induction to only 1 cycle of standard infusional cytarabine $100\text{mg}/\text{m}^2$ over 24hrs. daily $\times 7$ days and an anthracycline (daunorubicin, idarubicin, or mitoxantrone at standard doses). At count recovery or sooner if residual leukemia is present at the end of induction, 1 cycle of dose-adjusted high dose cytarabine can be administered (1-1.5gm/m² IV Q12hrs. on days 1,3, and 5, per standard of care).

1.3 Consolidation Therapy for Older Patients with AML.

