2. STUDY OBJECTIVES

Primary Objectives:

- To assess the safety and tolerability of delivering omacetaxine for consolidation in adult patients age 55 and older with acute myelogenous leukemia (AML) in first complete remission following induction chemotherapy.
- To assess the safety and tolerability of delivering omacetaxine for maintenance in adult patients age 55 and older with acute myelogenous leukemia (AML) in first complete remission following 3 consolidation courses with omacetaxine.

Secondary Objectives:

- To assess the duration of remission.
- To evaluate disease-free survival (DFS).
- To evaluate overall survival (OS).
- To assess for minimal residual disease (MRD) during consolidation and maintenance therapy with omacetaxine.

3. RESEARCH DESIGN AND METHODS:

3.1 Patient Selection:

3.1.1 Inclusion Criteria:

1. Diagnosis of AML including de novo, secondary, or with an antecedent hematologic disorder [AHD] according to the World Health Organization (WHO) criteria²⁵ (**Appendix A**).
2. Age \geq 55 years.
3. Patient eligible for standard induction chemotherapy based on ECOG PS and vital organ function at the discretion of the treating physician.
4. Patients who received 1-2 cycles of hypomethylating therapy (decitabine azacitidine) are eligible.
5. Provide signed written informed consent.
6. Be able to comply with study procedures and follow-up examinations.
7. Be non-fertile or not pregnant or lactating & agree to use birth control during the study through the end of last treatment visit.
8. Adequate renal and hepatic function **at the time of second registration**:
 - a. Total bilirubin \leq 1.5 x institutional Upper Limit of Normal (ULN); and
 - b. Aspartate aminotransferase (AST) and alanine aminotransferase (ALT) \leq 2.5 x ULN; and
 - c. Serum creatinine \leq 1.2 times the upper limit of normal.
9. ECOG performance \leq 2 (**Appendix B**) **at the time of second registration**:
10. Patients with a history of carcinoma in remission, on no therapy or on hormonal therapy for the adjuvant treatment of breast carcinoma or prostate carcinoma are included in the study.

3.1.2 Exclusion Criteria:

1. Diagnosis of acute promyelocytic leukemia (APL, French-American-British [FAB] classification M3 or WHO classification of APL with t (15;17)(q22;q12), (*PML/RARA* and variants).
2. Prior treatment with omacetaxine
3. Relapsed or refractory AML.

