Cycle #1: Cytarabine at $100\text{mgm}^2/\text{dose}$ via continuous infusion daily for 7 days, starting on day 1.

Daunorubicin, idarubicin, or mitoxantrone at standard dosing daily for 3 days, starting on day 1.

Cycle #2: Cytarabine 1- $1.5\text{gm}/\text{m}^2/\text{dose}$ IV twice daily on days 1, 3 and 5.

- Study specific evaluations during induction (See **Appendix D**)

B. Consolidation:

- Omacetaxine 1.25 mg/m² sub-cutaneously twice daily for 5 consecutive days every 28 (\pm 8) days for 3 cycles, provided that prior to the next planned treatment cycle, the patient's absolute neutrophil count (ANC) recovers to $\geq 1 \times 10^9/L$ and the platelet count recovers to $\geq 100 \times 10^9/L$. Patients with history of or suspected MDS prior to AML who fail to recover their ANC and platelets after induction chemotherapy, may start omacetaxine upon recovery to baseline pre-AML ANC and platelet count. Omacetaxine can be administered at Emory/Winship Cancer Institute or by self- injection at home.
- Evaluations during consolidation (see **Appendix E**)

C. Maintenance:

- Patients in continuous remission after 3 cycles of consolidation will receive maintenance omacetaxine 1.25mg/m² twice daily for 3 days, every 28 days for up to 6 cycles, provided that prior to the next planned treatment cycle, the patient's absolute neutrophil count (ANC) recovers to $\geq 1 \times 10^9/L$ and the platelet count recovers to $\geq 100 \times 10^9/L$. Patients with history of MDS prior to AML who fail to recover their ANC and platelets after induction chemotherapy, may start omacetaxine upon recovery to baseline pre-AML ANC and platelet count. Omacetaxine can be administered at Emory/Winship Cancer Institute or by self- injection at home.
- Evaluations during maintenance (see **Appendix F**)

D. Supportive Care (these guidelines are not protocol requirements as these as standard of care practices):

- Standard anti-microbial prophylaxis will be instituted for every patient enrolled in this study. Suggestions include: anti-viral (acyclovir or valacyclovir), anti-bacterial (fluoroquinolone, doxycycline, or standard alternative) and anti-fungal (azole or micafungin) prophylaxis will be initiated at the onset of neutropenia according to our institutional standard. Patients experiencing fever will be treated according to institutional practice, with blood cultures, imaging of suspected areas of infection, and empiric antibiotics targeted at the suspected cause of fever.

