Data quality will be monitored on an ongoing basis by random checks of CRFs following the Leukemia Working Group meetings. Co-investigators and staff will be trained on the conduct of the protocol and any additional training based on protocol amendments at the Hematology/Leukemia multi-disciplinary meetings, which meets regularly. Recording, grading, and reporting of adverse events will be carried out contemporaneously with each patient's clinic visit and will abide by the guidelines provided by the Winship Cancer Institute Clinical Trials Office. Deviations will be added to the Deviation Log, which is updated and reviewed at the Leukemia Working Group meetings.

The Principal investigator is responsible for sending a yearly IND summary report, which includes an update and status of the study and a tabulation of the AEs/ SAEs, as well as status of the study subjects, to the FDA. The PI is also responsible for collecting, reviewing, analyzing and reporting to the FDA and other investigators any potential serious risks that qualify for reporting under the FDA's IND Safety Reporting regulations at 21 CFR §312.32, .64 and 21 CFR § 320.31. In addition, the Sponsor-Investigator must copy the Emory IRB on

any such reports and include an analysis of whether the Sponsor-Investigator believes the event constitutes an Unanticipated Problem Involving Risks to Subjects or Others.

6. STATISTICAL CONSIDERATIONS:

Safety: Target omacetaxine dose is the dose that can be delivered to 70% patients without dose limiting toxicity (DLT) as defined above (section 3.3.4). Safety analysis will be conducted through continuous monitoring of AE/SAE. If 2 of the first 3 patients experience DLT, we stop the trial. After that, we stop the trial if there is evidence that the target probability of DLT exceeds 30% and the probability of falsely stopping the trial is 10% or less. The following table gives the minimum number of DLTs in order to stop the trial and the probability of falsely terminating the trial if in fact the probability of DLT is 30% calculated using the binomial distribution. For example, if after enrolling 6 patients, 4 or more experienced DLT, then we stop the trial and conclude that the target probability of DLT is more than 30%. The probability of incorrectly stopping the trial is 0.07.

To be considered safe, the upper limit of the one-sided 95% CI of DLT among 15 patients must not be greater than 30%.

Number of Patients	3	4	5	6	7	8	9	10	11	12	13	14	15

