Number of DLTs to Stop Trial	> 1	> 1	> 3	> 3	> 4	> 4	> 4	> 5	> 5	> 6	> 6	> 6	> 7
Probability of falsely terminating the trial		0.08	0.03	0.07	0.03	0.06	0.10	0.05	0.08	0.04	0.07	0.10	0.05

Feasibility: Feasibility is defined as delivery of 9 cycles of therapy for at least 2/3 of the patients. The proportion of patients with full treatment delivery will be estimated with an exact 95% confidence interval.

Futility: Based on our previous data showing a median relapse-free survival of 13.8 months, we will consider our consolidation/maintenance regimen futile if $\geq 80\%$ of those entering in CR relapse during consolidation/maintenance.

Kaplan-Meier curves will be used to estimate the distribution of time to relapse, relapse free survival, and overall survival.

Analysis of survival outcomes (OS, EFS, RFS) for patients who undergo transplantation in CR will include censoring and no censoring at the time of transplantation.

References:

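### The only 'safe' criterion is set on the 15 patients who start consolidation; it cannot support a safety claim for maintenance, a separate primary objective assessed only in the patients who get that far

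*Combined protocol and SAP*

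**What the plan says.** The document is the combined protocol and SAP.

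- **Objectives (section 2 and Synopsis).** Consolidation safety and maintenance safety are two separate primary objectives. The second reads: "To assess the safety and tolerability of delivering omacetaxine for maintenance in adult patients age 55 and older".
- **Cohort (Synopsis, sample size).** The investigational part enrols "15 patients in first complete remission after 2 inductions".
- **Who gets maintenance (section 3.3.1, C).** "Patients in continuous remission after 3 cycles of consolidation will receive maintenance omacetaxine". The number expected to reach this point is not given.
- **Safety verdict (section 6, Safety).** "To be considered safe, the upper limit of the one-sided 95% CI of DLT among 15 patients must not be greater than 30" per cent. The interval method, the DLT observation window and the phase are not stated. The stopping table is likewise indexed only by number of patients, up to 15.
- **Feasibility (section 6).** "Feasibility is defined as delivery of 9 cycles of therapy for at least 2/3 of the patients". Nine cycles are three of consolidation plus six of maintenance. This concerns delivery, not the DLT rate.

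**The concern.** The denominator suits the first primary objective but not the second. All 15 patients are exposed to consolidation; only those who complete it in remission are exposed to maintenance. Someone who relapses, goes to transplant or withdraws before maintenance, without a consolidation DLT, stays in the 15 as a DLT-free patient. Such losses dilute the maintenance DLT rate.

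The trial could then report 'safe' when its maintenance data do not exclude a 30% DLT rate, the plan's own limit. Section 1.6 presents this pilot as preparation for a phase II efficacy trial, so the maintenance schedule could be carried forward on a conclusion that the data in that phase do not support.

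**Working it through.** **1. The plan's own binomial figure.** Section 6 gives 0.07 as the chance of 4 or more DLTs in 6 patients at a 30% rate.

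15(0.3⁴)(0.7²) + 6(0.3⁵)(0.7) + 0.3⁶ = 0.0595 + 0.0102 + 0.0007 = 0.0705. This agrees.

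**2. What the 15-patient rule requires.** The exact one-sided 95% upper limit U for x DLTs in n patients solves P(Bin(n, U) ≤ x) = 0.05. For x = 0 this is U = 1 − 0.05^(1/n).

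- 0/15: 18.1%, passes
- 1/15: 27.9%, passes
- 2/15: 36.3%, fails

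'Safe' therefore means at most 1 DLT. If all 15 carry a 30% rate, P(≤1) = 0.7¹⁵ + 15(0.3)(0.7¹⁴) = 0.0047 + 0.0305 = 3.5%. As a per-patient test of the whole regimen, the rule holds its 5% level.

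**3. The same standard applied to maintenance entrants (m).**

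| m | limit, 0 DLTs | limit, 1 DLT |
|---|---|---|
| 8 | 31.2% | 47.1% |
| 9 | 28.3% | 42.9% |
| 10 | 25.9% | 39.4% |
| 12 | 22.1% | 33.9% |
| 13 | 20.6% | 31.6% |
| 14 | 19.3% | 29.7% |
| 15 | 18.1% | 27.9% |

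If the one permitted DLT occurs in maintenance, the entrants' limit exceeds 30% for every m of 13 or fewer. With 8 or fewer entrants, even 0 DLTs does not exclude 30%. In both cases the 15-patient rule still returns 'safe'.

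**4. How often this happens when the true maintenance DLT rate is 30%.** Let c be the per-patient consolidation DLT rate, with DLTs independent and m fixed:

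P(safe) = Bin(0; 15, c) × P(Bin(m, 0.3) ≤ 1) + Bin(1; 15, c) × P(Bin(m, 0.3) = 0)

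Example, m = 10:
- c = 0: 0.7¹⁰ + 10(0.3)(0.7⁹) = 0.0282 + 0.1211 = 14.9%.
- c = 5%: 0.4633 × 0.1493 + 0.3658 × 0.0282 = 8.0%.

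| m | c = 0 | c = 5% | c = 10% |
|---|---|---|---|
| 13 | 6.4% | 3.3% | 1.6% |
| 12 | 8.5% | 4.4% | 2.2% |
| 10 | 14.9% | 8.0% | 4.0% |

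The rates c are assumptions. The formula counts a patient with a DLT in both phases twice. Counting that patient once adds Bin(1; 15, c) × Bin(1; m, 0.3)/15. At c = 5% and m = 10 this is 0.3658 × 0.1211/15 = 0.003, and it is less at 12 or 13. The lowest printed stopping count is 2 DLTs, so early stopping does not alter these values.

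**5. Plausible m.** The documents give no figure.

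- *Relapse or death alone.* Assume exponential relapse-free survival, with a median of 11 months (section 1.2: "the median relapse-free survival was 11 months") or 13.8 months (section 6: "Based on our previous data showing a median relapse-free survival of 13.8 months"). Three consolidation cycles take 3 × 28 = 84 to 3 × 36 = 108 days. Retention 0.5^(t/median) runs from 0.80 to 0.87, or 12.0 to 13.1 of 15. Other losses would lower this.
- *Feasibility.* Nine cycles in at least 2/3 of 15 means at least 10 completers, so 10 is the fewest entrants with which the plan can meet its feasibility bar. Any dropout during maintenance means more must enter.

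**The case against.** The plan treats consolidation and maintenance as one regimen in one cohort: feasibility runs over all nine cycles, futility is stated for the combined regimen, and the sample size covers both. On that reading the 15-patient rule is a correct per-patient criterion for the strategy. The objective is only to assess safety, in a pilot that is otherwise descriptive. If the rule covers consolidation alone, which the missing DLT window allows, no false verdict on maintenance arises. Zero consolidation risk with 30% maintenance risk is also an extreme pairing, since maintenance gives the same dose on fewer days per cycle, although for up to six cycles rather than three.

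Much of this stands. It limits the size of the problem but does not remove it: on either reading the second primary objective is left without a criterion of its own, beside a 'safe' label that readers may extend to it.

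Two stronger inferences are tempting and are not supported.

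- *Very few patients will reach maintenance.* Section 1.2 reports that "6, 11, and 10 patients received 1, 2, and 3 consolidations with HiDAC, respectively", which might suggest that only 10 of 27 get through three cycles. That was a different drug, which this trial replaces in search of better tolerability. The same paragraph says standard consolidation was delivered in 80%, about 33 of the 41 in remission rather than 27, so even the denominator is unclear.
- *The error is commonly 25% or more.* It is 25.5% at 8 entrants and 42.0% at 6 (c = 0), but with fewer than 10 entrants the trial also fails its own feasibility definition.

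Nor does every early loss make 'safe' easier to reach. A patient lost through a consolidation DLT counts against the rule, and two such patients rule it out.

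**Conclusion.** The point holds in limited form. The 'safe' rule is valid for the regimen per patient and is not a valid test of maintenance. A reader might infer that the plan uses it to certify maintenance; the text never says so, but nothing in it prevents that use.

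At a 30% maintenance DLT rate the error exceeds 5% with 12–13 entrants only if consolidation toxicity is near zero. With 10 entrants it is 14.9% at no consolidation DLTs, 8.0% at 5%, and back under 5% at 10%.

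This rests on maintenance DLTs counting towards the 15-patient rule, on independent DLTs, on feasibility being judged over the 15, and on exact limits, the method the plan names for feasibility. With Wilson limits the thresholds shift (0 DLTs passes from 7 entrants, 1 DLT from 13) and the conclusion is the same. The change should be made because a stated decision rule has the wrong denominator for one primary objective.

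**What to change.** In section 6, Safety:

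1. State that the 15-patient 'safe' rule applies to the consolidation/maintenance regimen as a whole (or to consolidation only) and will not be used to claim that maintenance is safe.
2. For the maintenance objective, count DLTs among patients who start maintenance and report the rate with an exact one-sided 95% upper limit.
3. Claim that maintenance meets the 30% standard only if that limit is 30% or less: 0 DLTs with 9–13 entrants, at most 1 with 14–15, and not attainable with 8 or fewer. Otherwise report the result as descriptive.

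The cost is two or three sentences, with no added patients and no change to the stopping boundaries. The downside is that maintenance will often end as descriptive only. With 10 entrants, the chance of 0 DLTs is 0.95¹⁰ = 59.9%, 0.90¹⁰ = 34.9% or 0.80¹⁰ = 10.7% at true rates of 5, 10 or 20%. That reflects what so few patients can show.

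### In the Section 6 DLT stopping table, the false-stop probabilities for 13 and 14 patients should read 0.06 and 0.09, not 0.07 and 0.10

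*Combined protocol and SAP*

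**What the plan says.** The Safety paragraph of Section 6 sets up continuous monitoring of DLTs in up to 15 patients. After an initial rule for the first 3 patients, the trial stops on evidence that the DLT rate exceeds 30%, subject to the condition that "the probability of falsely stopping the trial is 10% or less". The table is said to give, for each number of patients, the minimum number of DLTs that stops the trial and "the probability of falsely terminating the trial if in fact the probability of DLT is 30% calculated using the binomial distribution".

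A worked example shows how to read a column: "if after enrolling 6 patients, 4 or more experienced DLT, then we stop the trial". The table prints this threshold as `> 3`. The text adds: "The probability of incorrectly stopping the trial is 0.07".

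In the row "Number of DLTs to Stop Trial", the entry is `> 6` for both 13 and 14 patients. In the row beneath, "Probability of falsely terminating the trial", the printed values are 0.07 and 0.10.

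**The concern.** The row states the error rate attached to each boundary, and it is what a reader sets against the 10% condition. If a cell does not follow from its own threshold and the stated method, then either the threshold or the probability is wrong. A wrong threshold would affect when the trial stops. A wrong probability affects only the description of the rule. The check therefore has to show whether the printed values at 13 and 14 patients are wrong, and which kind of error this is.

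**Working it through.** **Inputs, all from Section 6**
- DLT rate assumed for the row: p = 0.30.
- Method: binomial, one value for each number of patients n.
- Thresholds `> k` for n = 5 to 15: 3, 3, 4, 4, 4, 5, 5, 6, 6, 6, 7.
- Printed probabilities for n = 5 to 15: 0.03, 0.07, 0.03, 0.06, 0.10, 0.05, 0.08, 0.04, 0.07, 0.10, 0.05.
- Ceiling: 0.10.

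**Formula**

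P(X > k | n, p) = sum over x = k+1 to n of C(n, x) × p^x × (1 − p)^(n − x).

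**Step 1: reproduce the worked example.** With n = 6 and 4 or more DLTs:

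P(X ≥ 4) = 15 × 0.3^4 × 0.7^2 + 6 × 0.3^5 × 0.7 + 0.3^6 = 0.05954 + 0.01021 + 0.00073 = 0.0705 after rounding.

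The plan prints 0.07. This confirms both the method and the reading of `> 3` as 4 or more.

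**Step 2: the two cells.** The threshold `> 6` means 7 or more.

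- n = 13: 0.04415 (x = 7) + 0.01419 (x = 8) + 0.00338 (x = 9) + 0.00058 (x = 10) + 0.00007 (x = 11) + negligible terms = 0.0624, which rounds to 0.06. Printed: 0.07. Gap: 0.07 − 0.0624 = 0.0076.
- n = 14: 0.06181 (x = 7) + 0.02318 (x = 8) + 0.00662 (x = 9) + 0.00142 (x = 10) + 0.00022 (x = 11) + 0.00002 (x = 12) + negligible terms = 0.0933, which rounds to 0.09. Printed: 0.10. Gap: 0.10 − 0.0933 = 0.0067.

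**Step 3: the columns from 5 to 15 patients**

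| n | Threshold | Computed | Rounded | Printed |
|---|---|---|---|---|
| 5 | > 3 | 0.0308 | 0.03 | 0.03 |
| 6 | > 3 | 0.0705 | 0.07 | 0.07 |
| 7 | > 4 | 0.0288 | 0.03 | 0.03 |
| 8 | > 4 | 0.0580 | 0.06 | 0.06 |
| 9 | > 4 | 0.0988 | 0.10 | 0.10 |
| 10 | > 5 | 0.0473 | 0.05 | 0.05 |
| 11 | > 5 | 0.0782 | 0.08 | 0.08 |
| 12 | > 6 | 0.0386 | 0.04 | 0.04 |
| **13** | **> 6** | **0.0624** | **0.06** | **0.07** |
| **14** | **> 6** | **0.0933** | **0.09** | **0.10** |
| 15 | > 7 | 0.0500 | 0.05 | 0.05 |

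Nine of these eleven values agree. The values on either side of the pair (n = 12 and n = 15) agree too, so a shifted column does not explain the difference.

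**Step 4: other explanations**
- *Rounding up* gives 0.07 and 0.10, but it also gives 0.04, 0.08 and 0.06 at n = 5, 6 and 15, where 0.03, 0.07 and 0.05 are printed.
- *Counting k or more instead of more than k* gives 0.1654 and 0.2195, and it contradicts the worked example.
- *A normal approximation* with continuity correction gives 0.0578 and 0.0899. Without the correction it gives 0.0303 and 0.0512.
- *A Poisson approximation* gives 0.1005 and 0.1325.
- *A slightly higher DLT rate*: at 0.303 to 0.304 all eleven values round to those printed. The plan states 30%, however, and at 0.303 the value for n = 9 is 0.1025, above the plan's ceiling.

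**Step 5: do the thresholds move?** At n = 13 and n = 14 the threshold `> 6` gives 0.0624 and 0.0933, both within 0.10. The next lower threshold, `> 5`, gives 0.1654 and 0.2195, both above it. So `> 6` remains the smallest threshold that meets the condition.

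**The case against.** The strongest case against raising this is that nothing operational depends on it. The printed and the correct values all satisfy the 10% condition. The printed ones overstate the false-stop risk, so they hide no breach. The two cells apply only when at most two patients remain to be enrolled. A printed 0.10 also means nothing special, since the column for 9 patients prints 0.10 correctly (0.0988). All of this stands, and it limits the point to a correction of stated figures.

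A second objection is that each entry is a probability at one number of patients, while the text describes continuous monitoring. The cumulative false-stop probability at a 30% DLT rate over the printed boundaries is about 0.38, or about 0.28 if the column for 4 patients is read as `> 2`. This stands as well: correcting two cells does not turn the row into the probability that the trial as a whole stops falsely.

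Three stronger readings are tempting, and the documents do not support them.
- A reader might infer that the table as a whole cannot be reproduced. Nine of its twelve printed probabilities do reproduce. The exceptions are these two and the column for 4 patients.
- A reader might infer that the wrong figures would be reported if the trial stopped late. No section says that these values will be quoted.
- A reader might infer that regenerating the whole row is the same small edit. It is not. At the printed thresholds, a full regeneration gives 0.348 for 4 patients (printed 0.08) and 0.216 in the blank cell for 3 patients, both above 10%. Those columns raise a different question from a wrong digit.

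**Conclusion.** The probabilities printed for 13 and 14 patients do not follow from the stated binomial calculation. At a 30% DLT rate and the printed threshold they are 0.06 and 0.09. The error is 0.01 per cell at the table's precision, and less than 0.008 unrounded. The thresholds and the 10% condition are unaffected, so the matter is minor: two stated pointwise error rates are wrong, and no stopping decision is.

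The conclusion rests on the DLT rate of 30%, the binomial method and the reading of `> k` as at least k + 1, all of which Section 6 fixes. It also rests on the printed thresholds at 13 and 14 patients being the intended ones, which Step 5 supports. It says nothing about the column for 4 patients.

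**What to change.** In the Section 6 table, replace 0.07 with 0.06 for 13 patients and 0.10 with 0.09 for 14 patients. Leave the threshold `> 6` unchanged in both columns. The cost is two numbers in one table, with no change to the sample size, the boundaries or the conduct of the trial.

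Reconcile the threshold and the probability for 4 patients separately. That needs a decision by the investigators and should not be folded into this two-cell edit.
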